1.1 Cytomegalovirus infection

Induction therapy with an anti-interleukin monoclonal antibody (anti-IL2Ra) followed by maintenance therapy with tacrolimus (TAC), mycophenolate (MPA) and prednisone is currently considered the standard immunosuppressive regimen by most transplant centers and regulatory agencies. (1). Use of this regimen is associated with a low incidence of acute rejection and superior renal function at one year (2). However, recent data suggest that the use of anti-IL2Ra in kidney transplant recipients using TAC and MPA does not produce a significant additional reduction in the incidence of acute rejection. With this triple maintenance therapy, the addition of anti-IL2Ra induction can achieve an absolute risk reduction for acute rejection of only 1-4% in standard risk patients without improving graft or patient survival (3). A recent meta-analysis including 71 studies showed that the use of anti-thymocyte globulin (r-ATG) is associated with a 30% reduction in the incidence of biopsy-confirmed acute rejection, but with a 75% increase in malignancy and a 32% increase in increased incidence of CMV disease compared to anti-IL2Ra (4). In patients at high immunological risk, induction of r-ATG reduces the relative risk of acute rejection by almost 50% compared with anti-IL2Ra (3).

Cytomegalovirus (CMV) infection in solid organ transplant recipients is associated with “direct” and “indirect” effects that include graft rejection, predisposition to opportunistic fungal and bacterial infections, and higher incidence of malignancies, increasing morbidity and decreasing graft and patient survival. Risk factors associated with the development of CMV infection are the serological profile of recipients and donors, the type of immunosuppressive regimen, and the treatment of acute rejection (5). A recent review of 29 studies suggested that MPA-containing immunosuppression regimens are associated with an increased likelihood of developing CMV infection (6).

Universal prophylaxis and preemptive therapies are strategies used after solid organ transplantation to control CMV infection. The major advantage of prophylaxis is the inhibition of virus replication, preventing the direct and indirect effects of CMV infection. On the other hand, the antiviral drugs used can cause adverse reactions, are expensive, and a significant proportion of patients end up developing CMV infection after stopping prophylaxis. Preemptive therapy allows treatment to be indicated only

for patients with virus replication. Both strategies have advantages and disadvantages in terms of effectiveness, safety and costs to the health system (5).

Experimental and clinical data suggest that mTOR (mammalian target of rapamycin) inhibitors sirolimus (SRL) and everolimus (EVR) may limit CMV replication. A recent meta-analysis concluded that treatment with an mTOR inhibitor (imTOR), alone or in combination with calcineurin inhibitors, significantly reduces the incidence of CMV after organ transplantation, suggesting that with the use of an imTOR, prophylaxis for CMV infection could be expendable (7).

In a recent study we compared the incidence of CMV infection/disease in kidney transplant recipients receiving EVR or MPA and no pharmacological prophylaxis for CMV infection. 288 patients were randomized to receive a single 3 mg/kg dose of r-ATG, TAC, EVR and prednisone (r-ATG/EVR, n=85), basiliximab (BAS), TAC, EVR and prednisone (BAS/EVR, n=102) or BAS, TAC, MPA and prednisone (BAS/MPS, n=101). The incidence of CMV infection/disease was significantly lower in the everolimus-treated patient groups (r-ATG/EVR 4.7% vs. BAS/EVR 10.8% vs. BAS/MPS 37.6%, p<0.001). There were no differences in the incidence of acute rejection (9.4 vs. 18.6 vs. 15.8%, p=0.403), wound healing complications, delayed graft function and proteinuria. The estimated mean glomerular filtration rate was lower in BAS/EVR (65.7 ± 21.8 vs. 60.6 ± 20.9 vs. 69.5 ± 21.5 ml/min, p=0.021). The reduced incidence of CMV infection observed in this study suggests that even preemptive treatment may be restricted to only those patients at highest risk for CMV infection, further reducing the costs of transplant center management (8).

1.2 Objective

This study was designed to assess the influence of using SRL or EVR (controlled for their residual blood concentrations) with TAC (reduced residual blood concentrations) compared to MPA (fixed doses) with TAC (standard residual blood concentrations) with regard to efficacy and safety in de novo kidney transplant recipients.

The primary outcome is the incidence of CMV infection/disease, a relevant medical need in the absence of pharmacological prophylaxis due to its morbidity and costs incurred by the public health system. This outcome represents an attempt to reduce the negative influence of this infection on the outcome of the transplant and on the

management of health resources, provided that the other key variables of efficacy and safety of these immunosuppression regimens are not inferior to those demonstrated by standard treatment.

2. Research plan

2.1 Study design:

This prospective, randomized, single-center clinical study was designed to compare the safety and efficacy of three immunosuppressive regimens (Group 1, SRL) single-dose r-ATG, TAC, SRL, and prednisone; (Group 2, EVR) single dose of r-ATG, TAC, EVR and prednisone; (Group 3, MCF) single dose of r-ATG, TAC, MPA and prednisone.

The study was submitted to the local research ethics committee for approval and an informed consent form will be obtained from all patients. The study will be conducted within good clinical practice in accordance with the Declaration of Helsinki. Patients who meet the inclusion and exclusion criteria will be randomized within the first 24 hours after transplantation, in a 1:1:1 ratio and stratified according to the type of donor (deceased or living). All patients will be followed for 12 months or until graft loss.

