9.2 CMV infection and disease

- 9.2.1 CMV Infection:** evidence of asymptomatic replication of CMV.
- 9.2.2 CMV Disease:** evidence of CMV infection with related symptoms. CMV disease can be categorized as a syndrome (fever, malaise, leukopenia, or thrombocytopenia) or as an invasive disease with histological evidence.
- 9.2.3 Recurrent CMV disease/infection:** defined as a new episode of CMV infection after documented effective previous treatment (2 weekly negative antigenemia tests).
- 9.2.4 CMV replication:** will be confirmed by detection of CMV pp65 antigen by indirect immunofluorescence in peripheral blood leukocytes. The diagnosis of viral replication is confirmed by the presence of 10 or more positive cells per 200,000 peripheral blood leukocytes in asymptomatic patients or any number of positive cells in the presence of typical symptoms or in recipients with negative serology for CMV.
- 9.2.5 Preemptive strategy:** monitoring of CMV replication will be performed every 15 days between the third and 12 weeks after transplantation. Additional monitoring will be performed for 12 weeks after treatment for acute rejection.
- 9.2.6 Treatment of CMV disease/infection:** Patients will receive standard intravenous ganciclovir (5 mg/kg every 12 hours) corrected for renal function as per package insert recommendations. Monitoring of CMV replication will be carried out weekly. The duration of treatment will be extended by one week after the first negative antigenemia test. Consequently, the minimum duration of treatment will be 14 days. The duration of treatment for patients with invasive disease will be at least 21 days, being extended in the presence of a positive antigenemia test.

10 Statistical planning

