10.1 Sample size - main study

Primary outcome: cytomegalovirus infection or disease

For the primary outcome of cytomegalovirus infection, we calculated the sample required to show superiority of the experimental groups (EVR and SRL) over the control (MPA). For this calculation, we considered an incidence of 72% in the MPA group and an expected reduction of 50% (to 36%) in the experimental groups. For a margin of superiority of 0% and power of 90%, the total number of patients would be 42 in each group, considering 20% drop outs.

11 Reference

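### Planned follow-up ends at graft loss, so deaths and serious safety events after it are not planned to be observed; the effect on the CMV primary outcome is small

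*Combined protocol and SAP*

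**What the plan says.** Section 2.1 sets the length of observation: "All patients will be followed for 12 months or until graft loss". Section 1.2 names the endpoint, "The primary outcome is the incidence of CMV infection/disease", without a time point. It makes the value of a CMV benefit conditional on showing that "the other key variables of efficacy and safety of these immunosuppression regimens are not inferior" to those of standard treatment.

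Section 9.2.5 sets the CMV testing schedule: "monitoring of CMV replication will be performed every 15 days between the third and 12 weeks after transplantation". It adds: "Additional monitoring will be performed for 12 weeks after treatment for acute rejection".

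Section 10.1 plans on large CMV rates: "we considered an incidence of 72% in the MPA group" and "an expected reduction of 50% (to 36%) in the experimental groups".

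The documents state no analysis set, no rule for missing data, and no handling of graft loss or death in the CMV outcome. The only exclusion tied to graft loss is in the definition of delayed graft function (section 9.1), where losses from vascular thrombosis are left out.

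**The concern.** Stopping observation at graft loss is harmless only if the loss is unrelated to treatment and to what happens next. The documents give reasons to doubt the first. Section 1.1 links CMV to rejection and to poorer graft and patient survival, so fewer CMV infections could mean fewer lost grafts. Section 2.8 lists nephrotoxicity, slower renal recovery and wound problems for the sirolimus and everolimus regimens, which could act the other way. Graft loss may therefore differ between arms in either direction.

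The comparison most exposed is the one on safety and survival. If an experimental arm loses more grafts, more of its later deaths and serious events go unobserved, and it looks safer than it is. In a judgement of non-inferiority that gives false reassurance. If the mycophenolate arm loses more, the error runs against the new regimens.

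**Working it through.** **Inputs from the documents**
- Arm size: 50 (section 2.4 table), or 319 / 3 = about 106 (section 3, with 1:1:1 allocation from section 2.1). These figures and the 42 in section 10.1 do not agree, so both 50 and 106 are carried through.
- Planned CMV incidence: 72% mycophenolate, 36% sirolimus or everolimus (section 10.1).

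**Assumptions, because the documents give no figure**
- Graft loss within 12 months: 2-5% per arm.
- Two-sided alpha of 0.05.

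**The plan's own figure.** Unpooled two-proportion formula at 90% power: n = (1.960 + 1.282)² × (0.72 × 0.28 + 0.36 × 0.64) / 0.36² = 35.02. Multiplying by 1.2 gives 42.0, the stated number per group (dividing by 0.8 gives 43.8). The planning rates can therefore be taken as they stand. Section 10.1 does not say whether graft loss counts within its 20% dropout.

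**Patients affected**
- 50 per arm: 0.02 × 50 = 1.0 to 0.05 × 50 = 2.5, so about 1-3.
- 106 per arm: 0.02 × 106 = 2.1 to 0.05 × 106 = 5.3, so about 2-5.

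**Survival.** One unobserved death is 1/50 = 2.0 points or 1/106 = 0.9 points. The documents give no risk of death after graft loss, so an expected bias cannot be calculated. It cannot exceed the arm's graft-loss rate, here 2-5 points.

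**CMV.** Suppose 5% of an arm lose the graft before any CMV event, would have had the planned risk afterwards, and are scored as event-free:
- sirolimus or everolimus arm: 0.05 × 36% = 1.8 points understated, in favour of the new regimen;
- mycophenolate arm: 0.05 × 72% = 3.6 points understated, against the new regimens;
- equal loss in both: 0.95 × 36 = 34.2 points instead of 36, which is conservative.

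As an extreme, let every lost experimental patient have CMV and leave mycophenolate unchanged. The experimental rate is then 0.95 × 36% + 5% = 39.2%, and the difference is 32.8 points. Power (pooled variance) falls from 0.926 to 0.870 at 42 evaluable per arm and stays at about 0.999 at 106.

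**Timing.** Routine CMV testing runs from week 3 to week 12. A patient who loses the graft before week 3 has no scheduled test under the follow-up rule. A loss between weeks 3 and 12 cuts testing short. A later loss costs no scheduled test unless it falls in the 12 weeks after treated rejection. The CMV bounds above are therefore upper limits, driven mainly by losses before week 12.

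**The case against.** A reader might infer that patients with graft loss leave the analysis, so that the comparison is no longer of all randomised patients. The documents do not say that. The end of observation is not removal from the denominator: these patients can be analysed with their events up to graft loss, or with graft loss as a competing event. The section 9.1 exclusion applies to delayed graft function only. The silence on the analysis set is a gap, not a stated exclusion.

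A reader might also infer that later deaths will certainly never be counted, or that these patients carry the greatest risk of death. Neither is documented. The follow-up sentence means that later events are not planned to be observed; no passage forbids obtaining vital status. Nothing in the documents ranks mortality risk after graft loss.

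Two further objections have force. Patient survival is not named as an outcome in this trial: section 1.2 speaks only of unnamed key variables, and section 10.1 gives a calculation for CMV alone. And if efficacy were judged by a composite that includes graft loss, these patients would already count as failures. Both limit the size of the point. Neither removes it, because deaths and serious adverse events belong to any safety comparison of immunosuppressive regimens, and the follow-up rule as written stops collecting them.

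**Conclusion.** The point stands for safety and survival and is worth acting on. Section 2.1 states a rule that ends observation at an event treatment may affect, and nothing elsewhere restores data collection. At an assumed 2-5% graft loss it touches a handful of patients per arm, but with arms of 50 to 106 a single unobserved death moves a 12-month rate by 2.0 to 0.9 points. The actual bias is unknown, since neither the graft-loss rate nor the risk afterwards is given.

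For the CMV primary outcome the effect is minor: at most 1.8 points in the direction that favours sirolimus or everolimus at 5% loss, against 36 planned. It does not threaten the superiority comparison. The documents do not support a claim that randomised patients are excluded from that comparison.

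**What to change.** Change section 2.1 so that every randomised patient is followed to month 12 regardless of graft loss, with follow-up ending early only at death or withdrawal of consent. Record vital status, serious safety events and any diagnosed CMV infection or disease over that period.

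In section 10, state that all randomised patients stay in the analysis as allocated. Give the time point for the CMV outcome. Treat death as a competing event, and graft loss likewise if CMV observation stops there, for example with cumulative incidence functions by arm.

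The cost is a small amount of extra data retrieval in a few patients at one centre. Section 3 reports inclusion in the past tense, so some of it may have to be retrospective. CMV capture after graft loss will be less sensitive than scheduled antigenemia testing: a single check at month 12 cannot recover an asymptomatic episode that has passed. The gain is therefore mainly in survival and safety, and any report should say so.

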2.2 Treatment Groups

Grupo 1, SRL: r-ATG/SRL/TAC/Prednisone

Patients will receive an initial dose of 0.05 mg/kg BID of TAC adjusted from day 3 to maintain a total blood concentration of TAC between 3-5 ng/mL. Patients will receive an initial dose of 3 mg QD sirolimus adjusted from day 3 to maintain a concentration between 4-8 ng/mL.

Grupo 2, EVR: r-ATG/ EVR /TAC/Prednisone

Patients will receive an initial dose of 0.05 mg/kg BID of TAC adjusted from day 3 to maintain a total blood concentration of TAC between 3-5 ng/mL. Patients will receive an initial dose of 1.5mg BID everolimus adjusted from day 3 to maintain a concentration between 4-8 ng/mL.

Grupo 3, MCF: r-ATG/Mycophenolate/TAC/Prednisone

Patients will receive an initial dose of 0.1 mg/kg BID of TAC adjusted from day 4 to maintain a total blood concentration of TAC between 5-10 ng/mL. Patients will receive fixed doses of mycophenolate (MMF, 1 g BID; MPS, 720 mg BID).

2.3 Induction therapy

All patients will receive 1 g of methylprednisolone before graft revascularization. All patients will receive a single dose of 3 mg/kg body weight of anti-thymocyte globulin administered intravenously over 6-8 hours, starting within the first 24 hours after graft revascularization. Pre-treatment will be performed with hydrocortisone and dipyrone, according to local practice.

2.4 Maintenance therapy

The first dose of all immunosuppressive drugs will be administered within the first 24 hours after graft revascularization.

Treatment group	Drug	Initial dose	Concentration (ng/ml)
Group 1, SRL (n=50)	r-ATG	3 mg/Kg IV day 1	NA
	TAC	0,05 mg/kg BID	3-5
	Sirolimus	3 mg QD	4-8
Group 2, EVR (n=50)	r-ATG	3 mg/Kg IV day 1	NA
	TAC	0,05 mg/kg BID	3-5
	EVR	1,5 mg BID	4-8
Group 3, MCF (n=50)	r-ATG	3 mg/Kg IV day 1	NA
	TAC	0,1 mg/kg BID	5-10
	MMF ou MPS	1000 mg BID	NA
		720 mg BID	NA

The primary use of other immunosuppressive drugs is prohibited. However, switching to another immunosuppressive drug is permitted both due to lack of efficacy (documented episodes of acute rejection) and the occurrence of adverse events.

At the 6 month visit, all patients who are eligible, according to pre-established criteria, will simplify the TAC and EVR dosing schedule of BID for QD, maintaining the same daily dose in a single dose to achieve blood concentrations between 3 and 5 ng/ ml.

2.5 Corticosteroids

All patients will receive 0.5 mg/kg/day of prednisone with a maximum dose of 30 mg starting on day 1. Doses of prednisone will be reduced to 20 mg/day on day 7, 15 mg/day on day 14, 10 mg /day on day 21 and 5 mg/day on day 30, which will be maintained for at least 12 months.

2.6 Study rationale

The use of a single dose of 3 mg/kg of anti-thymocyte globulin in induction therapy is currently standard in our institution, consistently providing an incidence of acute rejection of less than 10% at the end of the first year of transplantation. However, patients receiving this therapy and induction combined with standard maintenance therapy (TAC, mycophenolate, and prednisone) have a high incidence (60%) of CMV infection/disease. Using sirolimus or everolimus instead of mycophenolate may maintain efficacy for preventing acute rejection while reducing the incidence of CMV infection/disease.

Adherence to immunosuppressive treatment is one of the factors with an important influence on long-term renal graft survival (9). The incidence of non-adherence to treatment varies among different populations of kidney transplant recipients, reaching 60% in some cases. Constant education, technological facilities to alert the patient and simplification of medication dosage are strategies that can improve treatment adherence (10).

Among the maintenance immunosuppressive regimens currently available to kidney transplant recipients, none offers the possibility of once-daily administration of all drugs to facilitate adherence to treatment.

2.7 Rationale of drug doses and concentrations

Doses and concentrations of TAC combined with sirolimus or everolimus were based on prospective multicenter studies and also on the experience of our transplant center. Sirolimus was used in these studies as a loading dose because of its longer half-life. Recent evidence suggests an association of this loading dose with a higher incidence of wound complications. The effectiveness of using r-ATG induction therapy may justify not using this loading dose. Sirolimus and everolimus belong to the same therapeutic class of immunosuppressants (mTOR inhibitors). A comparative analysis of published works suggests that the target concentrations of these two drugs are very close. Thus, the initial dose chosen for sirolimus and everolimus was 3 mg QD and the target residual blood concentrations will be similar, between 4-8 ng/ml.

Although it is assumed that the use of SRL or EVR can provide similar results, some uncertainties justify the performance of this study. Due to its prolonged elimination half-life, SRL is administered as a single daily dose, usually after a loading dose (11). Recent studies suggest that this loading dose may be associated with the higher incidence of wound complications observed in the initial studies (12). Another important point is that the therapeutic concentration of SRL has not been clearly determined through prospective studies using current immunosuppression regimens (13). The evaluation of this regimen is therefore essential for its wider use, when indicated, especially considering the ease of dosage.

Doses and concentrations of TAC and MPA correspond to those obtained in the largest prospective study in kidney transplant recipients and accepted as “standard of care” by regulatory agencies (14).

Blood concentrations of SRL and EVR will be determined by HPLC and blood concentrations of TAC will be determined by chemiluminescence microparticle immunoassay (CMIA).

2.8 Risks/benefits

Sirolimus or everolimus regimens may reduce the incidence of viral infections, including CMV, herpes, and polyomavirus infection. In addition, there may be a reduction in the incidence of fungal and bacterial infections, a lower incidence of

diarrhea and myelotoxicity associated with the use of MPA. On the other hand, these regimens are associated with slow recovery of renal function, higher incidence of wound complications, edema, nephrotoxicity, proteinuria, and dyslipidemia. All of these adverse reactions are associated with disproportionately high concentrations of TAC and sirolimus or everolimus.

3. Population

A sample calculation was performed for each outcome to be analyzed in this study. The complete description is in section 10. "Statistical planning".

A total of 319 patients were included in the study.

3.1 Inclusion criteria

1. Recipients, adults of both genders, of the first standard living or deceased donor kidney transplant;
2. Patients who agree to participate in the study and sign the informed consent form

3.2 Exclusion criteria

1. Recipients with a medical history of nephrotic syndrome or focal segmental glomerulosclerosis confirmed as the etiology of end-stage renal disease;
2. Recipients with difficulty understanding chronic kidney disease and its treatment alternatives;
3. Recipients with anticipated difficulty in adhering to treatment with immunosuppressive drugs;
4. Retransplant recipients;
5. Multi-organ receptors;
6. Recipients with $BMI > 30 \text{ kg/m}^2$;
7. Deceased donor kidney recipients with $KDPI > 80\%$;
8. Deceased donor kidney recipients with cold ischemia time greater than 24 hours;
9. Patients without specific antibodies against the donor.

10. Women of childbearing age who do not commit to using contraceptive methods (condoms or oral contraceptives).
11. Patients using immunosuppressive therapy before transplantation, except for low-dose prednisone;
12. Patients with severe uncontrolled dyslipidemia;
13. Patients who have a known contraindication for the administration of any of the immunosuppressive drugs provided for in this study;

4. Randomization

At the baseline visit, within 24 hours after vascular anastomosis, all eligible patients will be randomized using a numerical sequence, stratified by type of donor (deceased or living), generated by a computer program and placed in opaque envelopes. The open envelope, designated the treatment allocated to the patient, will be kept in your record.

5. Prophylaxis against infections

No pharmacological prophylaxis will be used against CMV infection. Preventive treatment will be carried out by monitoring virus replication detected by the antigenemia test. All patients will use oral nystatin for at least 30 days as prophylaxis of fungal infections. All patients will receive prophylaxis of parasitic infections with albendazole. All patients will use oral trimethoprim-sulfamethoxazole as prophylaxis of pneumocystis jirovecii or urinary tract infection.

9. Definitions

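### Exclusion criterion 9, as printed, admits only recipients who have antibodies against the donor, a population the protocol describes nowhere else; the intended criterion must be stated and the one applied confirmed

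*Combined protocol and SAP*

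**What the plan says.** Item 9 of section 3.2 (Exclusion criteria) reads, in full, "Patients without specific antibodies against the donor". The item does not define the antibodies by assay or cut-off.

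The list decides who enters the trial. Section 2.1 states: "Patients who meet the inclusion and exclusion criteria will be randomized within the first 24 hours after transplantation". Section 4 repeats the point: "all eligible patients will be randomized using a numerical sequence".

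The population is described elsewhere as follows:

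- Section 1.2 frames the comparison "with regard to efficacy and safety in de novo kidney transplant recipients".
- Section 3.1, item 1, admits "Recipients, adults of both genders, of the first standard living or deceased donor kidney transplant".
- Section 2.6 describes the centre's single-dose r-ATG induction as "consistently providing an incidence of acute rejection of less than 10% at the end of the first year of transplantation".
- Section 1.1 has the only remark on raised immunological risk, as literature background: "In patients at high immunological risk, induction of r-ATG reduces the relative risk of acute rejection by almost 50% compared with anti-IL2Ra".

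Section 3 gives 319 patients as included.

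**The concern.** An exclusion worded in the negative admits the opposite group. Followed exactly, item 9 would confine the trial to recipients with antibodies against their donor. If that were intended, it would be a defining feature of the study and should appear in the objective, the rationale or the inclusion criteria. It appears in none of them.

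Two situations are possible, and the documents do not show which occurred. Either item 9 was followed, and the trial enrolled a population that the protocol does not otherwise describe; or another criterion was used, and the printed protocol misstates who was eligible. In the second case, every antibody-negative patient enrolled is a deviation from the printed text. Either way, a reader cannot tell to whom the results apply.

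**Working it through.** No arithmetic beyond a count applies, and the plan has no figure of its own on this point to reproduce. The check is a logical reading followed by a comparison of sections.

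1. **Logic of the line.** Let A mean that the recipient has antibodies against the donor. Item 9 excludes not-A, so a patient can be eligible only if A holds. No reading of the sentence under its present heading gives another result.

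2. **Does another line offset it?** Eligibility lines: 2 (section 3.1) + 13 (section 3.2) = 15. Lines that mention antibodies against the donor: 1, which is item 9 itself. The other 12 exclusions read normally, including item 10 on contraception, which is also worded in the negative. The list as a whole has therefore not been inverted.

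3. **Does any other section describe an antibody-positive trial?**
   - Section 1.2: de novo recipients, with no mention of antibody status.
   - Section 3.1: first standard transplants, with no antibody requirement. Section 3.2, item 4, also removes retransplants.
   - Section 2.6: rests on the centre's standard induction and a rejection incidence below 10%, with no reference to antibody-positive patients.
   - Sections 2.1 and 4: stratification by donor type only.
   - Section 9: defines delayed graft function and CMV events. Neither there nor elsewhere in the available text is there an antibody assay, threshold or monitoring schedule.
   - Section 1.1: the sentence on high immunological risk reports published results for r-ATG and does not define this trial's population.

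4. **Is the mismatch a direct contradiction?** No. None of these sections mentions donor antibodies, and a first-transplant recipient can have them. The mismatch is one of context: a restriction this strong stands alone in one line and is supported by nothing around it.

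5. **Can the effect be sized?** No. Antibody status is not given for screened or enrolled patients. The sample-size inputs in section 10.1 (72% against 36%, 90% power, 42 per group) make no reference to antibody status. Whether those rates would hold in an antibody-positive population cannot be judged from the documents.

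**The case against.** The strongest reply is that this is a slip of wording, not a conflict in the plan. The English shows signs of translation: non-English words remain in the arm labels of section 2.2 and the dosing table of section 2.4, and that table uses decimal commas. If the centre worked from a text in another language, item 9 may be wrong only in this version. The neighbouring exclusions (retransplantation, KDPI above 80%, cold ischaemia beyond 24 hours) make it less likely that a reader would take item 9 as a deliberate restriction to antibody-positive recipients. The sections set against it are silent on antibodies, and silence is not contradiction. The available text also jumps from section 5 to section 9, so only that text could be searched. Finally, no effect on the primary comparison is shown, and checking records for 319 included patients, plus those screened out, is more than a one-line edit.

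Much of this stands. A translation slip is plausible, the mismatch is contextual, the search is limited to the available text, there is no between-arm bias, and the records check carries a real cost. None of it removes the problem. The printed line is an operative eligibility rule, no other line corrects it, and a reader should not have to take a criterion as its opposite. A likely origin for the error does not show which criterion was applied.

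**Conclusion.** The concern holds. As printed, item 9 leaves only antibody-positive recipients eligible, and nothing else in the available protocol describes such a trial. It should be fixed. The consequence is for eligibility, the description of the population and generalisability. The internal comparison is not biased, because the rule applies before allocation and equally to all three arms. The size of the effect is unknown and cannot be derived from the documents.

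That the line is inverted or misplaced is probable but not proven. This conclusion does not depend on it, and it takes no position on which antibody criterion the trial should have used. It assumes only that item 9 is complete as printed (there is no sign of redaction or lost text around it) and that sections missing from the available text contain no separate antibody rule. If they do contain one, item 9 would still have to be reconciled with it.

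**What to change.** - State the intended antibody criterion explicitly, including what counts as a specific antibody against the donor, which item 9 leaves undefined.
- Confirm from the screening records which criterion was applied.
- If the printed text differs from the confirmed criterion, issue a dated correction that reconciles item 9 with the population described in sections 3.1 and 2.6.
- Report any patients enrolled or excluded contrary to the confirmed criterion.

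The correction is one dated line. The larger cost is the check of screening records, which covers the 319 included patients and an unstated number screened out. No change to the design, the sample size or the comparison of arms follows from the clarification itself.
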